##### ***Prior to Photofrin® injection***

1. Reevaluate eligibility criteria.
2. Vital signs (pulse, blood pressure, temperature, and respiration rate).
3. Body weight.
4. Review instructions on how to manage light exposure.
5. Record concomitant medications and adverse events.

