## 8.2. Pre-existing Medical Conditions

Any pre-existing medical condition (including findings from physical examination), which does not worsen in duration, intensity or frequency during the study, is not an AE. These pre-existing medical conditions should be adequately documented in the medical history/current illnesses of the CRF and any other appropriate ancillary documents. Pre-existing medical conditions which worsen after ICF signature will be recorded as an AE on the Adverse Event Form of the CRF.

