#### 8.4.1. Assessment and Recording

An AE, whether or not considered to be causally related to the treatment, must be promptly documented and recorded. At each study visit, after the subject has had an opportunity to spontaneously mention any problems, the investigator should inquire about AEs by asking the appropriate open questions. In addition to straightforward subject observation (e.g., headache, nausea, etc.), AEs will also be documented from any data collected in the CRF (e.g., laboratory values, physical examination findings, ECG changes, etc.) or other documents that are relevant to the safety of the subject.

At each follow-up visit or assessment by phone or otherwise, all AEs, whether observed by the investigator or other professional collaborators, or reported by the subject spontaneously or in response to an open question, will be recorded on the Adverse Event Form included in the CRF with the following information.

- Name of the AE: Name should be a medical term. When possible, the investigator should differentiate an illness entity from isolated symptoms or signs. For instance, the term “flu” should be recorded instead of listing all the flu-related symptoms. Where a differentiation is not possible, symptoms and signs should be separately recorded and evaluated as adverse events.
- Date of onset of the AE.
- Intensity: Event intensity will be assessed according to the CTCAE. If not described in the CTCAE, the intensity should be assessed according to the following categories: *Mild* (noticeable to the subject, does not interfere with the subject’s daily activities, usually does not require additional therapy, dose reduction, or discontinuation of the study); *Moderate* (interferes with the subject’s daily activities, possibly requires additional therapy, but does not require discontinuation of the study); *Severe* (severely limits the subject’s daily activities and may require discontinuation of the study); *Life-threatening*; *Death*.
- Date of resolution (or statement that the event is continuing).
- Action taken (e.g., concomitant medication or adjunctive therapy given will be recorded on the Concomitant Medications Form or the Adjunctive Therapy Form of the CRF, respectively).
- Outcome defined as resolved, resolving, ongoing, worsening, death, or unknown.
- Whether the event meets the definition of a SAE (see Section 8.1).

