S=Screening; E=Enrolment; a Will include radiology/pathology reports confirming primary or metastatic solid tumor in peripheral lung and thoracic surgeon confirming the tumor resectability; b On Day 1, vital signs (pulse, blood pressure, temperature, and respiration rate) to be performed prior to Photofrin® injection and repeated at 15 and 30 minutes, 1, 2, 4, and 8 hours after injection. Afterwards, vital signs to be assessed once, prior to all other procedures being performed; c If not done up to 90 days prior to ICF signature; d If not done up to 30 days prior to ICF signature; e Clinical labs to include hematology and chemistry as specified in Appendix 13-4; f For females of childbearing potential only, who must agree to use acceptable contraceptive method for 90 days post Photofrin® injection; g Subject to be discharged from the 48-hour hospital stay after the Chest X-ray and other safety evaluations indicating that the subject is stable and able to be discharged; otherwise, the subject's hospital stay may be extended to 72 hours or until the subject is stable for discharge; h All AEs to be recorded from the time of ICF signature; i All medications and adjunctive therapies/procedures to be recorded 30 days prior to screening and throughout the study.

---

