5.4.11.1 Adverse Events

Adverse Events will be coded using the Medical Dictionary of Regulatory Activities (MedDRA version 20.0) AE coding system for purpose of summarization.

Events collected at the "NCS Events" CRF page will be summarized together with Adverse Events, but excluded from analyses by CTCAE grade and relationship to study drug, since these data points are not captured for NCS events.

An AE will be defined as treatment-emergent (TEAE) if its date of onset is on or after the date of the study drug (PHO) administration.

An AE will be defined as treatment-related if its relationship to the study drug is recorded as "Reasonable Possibility" on the CRF.

An overall summary of number and percentage of subjects with at least one AE, TEAE, serious TEAE, treatment-related TEAE, serious treatment-related TEAE, TEAE leading to discontinuation and fatal TEAE will be presented.

A summary of the frequency (number and percentage of subjects) of TEAEs will be presented by system organ class and preferred term. One-sided 95% upper confidence limit will be computed for each AE percentage via exact (Clopper-Pearson) method for binomial proportion. Adverse events will also be analyzed by their CTCAE grade (1 to 5) and relationship to study drug (related or not related).

A subject experiencing the same AE multiple times will be counted only once for that preferred term. Similarly, if a subject experiences multiple AEs (preferred terms) within the same system organ class, then that subject will be counted only once for that system organ class. When summarizing by CTCAE grade and relationship, only event with highest grade or relationship will be counted. All AEs will be presented in alphabetical order of SOC and preferred terms.

Skin photosensitivity is an adverse event of special interest (AESI). Skin photosensitivity will be summarized separately by SOC and preferred term as well as by SOC, preferred term and CTCAE grade.

All information pertaining to adverse events noted during the study will be listed by subject, detailing verbatim term given by the investigator, preferred term, system organ class, start date, stop date, CTCAE grade, outcome, action taken and drug relatedness. Separate listings will be created for Serious TEAEs, TEAEs leading to study drug discontinuation and skin photosensitivity events.

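### The SAP's treatment-emergent rule has no worsening clause, so an AE that starts after consent but before the injection date and worsens afterwards is left out of the TEAE tables

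*SAP*

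**What the plan says.** SAP section 5.4.11.1 applies a single test. An AE is "treatment-emergent (TEAE) if its date of onset is on or after the date of the study drug (PHO) administration". The test uses a calendar date only and does not mention an increase in grade or seriousness.

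The main incidence table rests on that definition: "A summary of the frequency (number and percentage of subjects) of TEAEs will be presented by system organ class and preferred term". The exact one-sided 95% upper limits are specified directly after it. In the overall summary, one row counts all AEs; the serious, treatment-related, discontinuation and fatal rows count TEAEs only. The separate listing of serious events is also limited to TEAEs.

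Four parts of the protocol decide what the rule works on:

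- Appendix 13-1, footnote h, sets the start of collection: "All AEs to be recorded from the time of ICF signature".
- Section 8.4.1 lists the items recorded for each AE. One is "Date of onset of the AE"; another is "Outcome defined as resolved, resolving, ongoing, worsening, death, or unknown". No date of grade change is listed.
- Section 8.2 contains the general rule on worsening: "Pre-existing medical conditions which worsen after ICF signature will be recorded as an AE". It concerns conditions that were present before consent.
- Section 8.3 makes a laboratory value an AE when it is Grade 3 or 4 and significantly worse than at pretreatment. This is not confined to abnormalities that pre-date consent.

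**The concern.** Collection of AEs starts at consent, but the TEAE window opens on the injection date. An AE can therefore begin before exposure, still be present at injection, and become worse because of Photofrin or PDT. The usual purpose of a treatment-emergent definition is to catch both new events and worsening under treatment. This one catches only new events.

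If worsening stays on the existing record, that record keeps its pre-injection onset date. The event then fails the TEAE test even if it is now Grade 3 or higher, serious or fatal, and even if the investigator judges it related. Safety is the primary objective, and the tables that break AEs down by term and by seriousness are the ones built on TEAEs.

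**Working it through.** **Inputs.** Planned N = 10 (protocol section 10.1, SAP section 3.1). Schedule: screening Days -30 to -1, enrollment Day 0, injection Day 1, PDT Day 3 (protocol Appendix 13-1). TEAE rule: SAP section 5.4.11.1. Interval: exact binomial, one-sided 95% upper limit.

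**1. The plan's own limits.** For x subjects with the event out of n, the upper limit U solves P(X ≤ x | n, U) = 0.05, which is the 0.95 quantile of a Beta(x+1, n−x) distribution. With n = 10:

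- x = 0: U = 1 − 0.05^(1/10) = 0.2589
- x = 1: (1−U)^10 + 10·U·(1−U)^9 = 0.05 gives U = 0.3942
- x = 2, 3, 4, 5: U = 0.5069, 0.6066, 0.6965, 0.7776

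Rounded, these are the plan's 0.26, 0.39, 0.51, 0.61, 0.70 and 0.78. The figures are right; what is in question is the count x that enters them.

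**2. The exposed window.** With injection the day after enrollment, consent precedes it by between 1 − (−1) = 2 and 1 − (−30) = 31 days. Only onsets from consent to the day before injection are exposed.

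**3. The rule applied to four hypothetical AEs**, each kept on one record:

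- Onset 10 days before injection, worse on Day 4: not a TEAE.
- Onset the day before injection, worse after PDT: not a TEAE.
- Onset on Day 1 before the injection is given: TEAE.
- Onset on Day 2, worse after PDT on Day 3: TEAE.

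The first two are the gap. The fourth shows that an AE starting between injection and PDT is already counted. The third is a small error in the other direction.

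**4. Does another rule close the gap?** Protocol section 8.2 does not, because an AE that began after consent is not a condition that pre-dates it. Section 8.3 helps for laboratory values only, and does not say what happens when the abnormality is already an open AE. Section 8.4.1 treats worsening as an outcome of the AE being recorded. Neither document says that a rise in grade starts a new record with a new onset date.

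**5. Size.** Assume one of 10 subjects has such an event and no other subject has that term. Counting the worsening gives 1/10 with upper limit 0.39; the SAP rule gives 0/10 with 0.26. With two such subjects the change is from 2/10 (0.51) to 0/10 (0.26). The plan's worked example turns on this step: zero events puts the limit below a historical radiofrequency ablation rate of 0.27 (0.26 < 0.27), and one event does not (0.39 > 0.27).

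**The case against.** The strongest reply is that little is lost. The event remains in the all-AE row and in the by-subject listing with its start date, grade, outcome and relatedness, and with about 10 subjects every line can be read. The analyses by grade and relationship speak of adverse events, so they may not be limited to TEAEs. SAEs are reported within 24 hours from consent onward, the suspension rule is written in terms of PDT-related SAEs, and a DSMB reviews safety data. All of this stands and limits the consequence. It does not restore the event to the tables and rows that are explicitly TEAE-only.

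A second reply is that the mechanism is partly inferred. Section 8.4.1 does not forbid a second record, and the CRF completion guideline announced in protocol section 10.2 may require one. That is fair, but the SAP does not refer to any such rule.

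A reader might also infer more than the documents support:

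- That any AE starting after consent and worsening after treatment is lost. Onsets on or after the injection date are TEAEs.
- That post-PDT worsening disappears from the primary safety result. The primary endpoint is incidence of AEs, and the event stays in the all-AE row.
- That the same harm is counted or lost according to which side of consent it began. Section 8.2 does not say which onset date a worsened pre-existing condition receives.
- That the problem will be common because patients often have respiratory findings at entry. The documents give no such frequency, and findings present before consent come under section 8.2.
- That Day 1 handling is an equally serious fault. AEs are collected before the injection that day ("Record concomitant medications and adverse events"), and a date-only rule counts them as TEAEs, but this errs only toward over-counting harm.

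**Conclusion.** The gap is real but narrow. It affects AEs that begin after consent and before the injection date and then increase in grade, or become serious or fatal, after injection or PDT. Unless the site opens a new record, these are left out of the TEAE table by system organ class and preferred term with its upper limits, of the serious, related, discontinuation and fatal TEAE rows, and of the serious TEAE listing.

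The conclusion assumes that worsening stays on the existing record, which the AE items in the protocol suggest but the unseen CRF guideline could change. How often it would happen is unknown; the shift from 0.39 to 0.26 is what one case would do to one term. No decision rule in the trial depends on it. It should be fixed before analysis, because the rule as written gives a wrong count in the main safety tables and is easy to correct.

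**What to change.** In SAP section 5.4.11.1, define a TEAE as an AE that starts on or after the date of Photofrin administration, or that starts earlier and increases in CTCAE grade or becomes serious on or after that date.

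The wording alone is not enough, because no date of grade change is listed among the AE items. Sites should enter post-injection worsening of an ongoing AE as a new record dated at the worsening. Because the SAP counts a subject once per preferred term, splitting a record does not inflate subject counts.

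The SAP is dated April 10, 2018, and the protocol planned enrollment from Q2 2017 to Q1 2018, so part of this may be retrospective. Existing AEs with onset before injection should be queried before analysis; with about 10 subjects there should be few.

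Optional and minor: flag Day 1 AEs known to precede the injection and exclude them, treating unknown timing as after.

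The cost is one SAP sentence, one line of site guidance and some queries. The downside is that a few more events may count as TEAEs.

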5. STATISTICAL METHODOLOGY

5.1 General Considerations

All statistical evaluations will be conducted using SAS® version 9.4 or higher (SAS® Institute, Cary, North Carolina). All tables, figures and listings will be produced in landscape format.

In general, all data will be listed by subject and visit/time point where appropriate. The total number of subjects under the stated population (N) will be displayed in the header of summary tables.

Data will be summarized using descriptive statistics for continuous variables. Unless otherwise specified, descriptive statistics will include number of subjects, mean, standard deviation, minimum, median and maximum. In case of n<2, where n indicates the number of evaluable subjects at the particular time point, the standard deviation will be empty. The statistic "Missing" will also be presented as the number of missing entries/subjects, if any at that visit/timepoint, and presented as a summary statistic only when non-zero. The minimum and maximum statistics will be presented to the same number of decimal places as the original data. The mean and median will be presented to one more decimal place than the original data, whereas the standard deviation will be presented to two more decimal places than the original data.

In summary tables of categorical variables, counts and percentages will be used. The count [n] indicates the actual number of subjects with a particular value of a variable or event, which should always be less than or equal to the total number of subjects with non-missing value of the variable or event [M]. Percentage will be obtained by: % = (n/M)*100. Unless otherwise stated, all percentages will be expressed to one decimal place.

In by-visit summary tables only scheduled visits/timepoints will be summarized. In listings all visits and timepoints with any data collected, including both scheduled and unscheduled ones and early termination visits, will be included.

The closest non-missing measurement (whether from scheduled or unscheduled visit) taken prior to the administration of the study drug (PHO) will be considered as the baseline value. The change from baseline values will be derived for each subject as the post-baseline evaluation minus the baseline evaluation.

Study days will be calculated as the number of days from the date of the study drug administration:

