5.4 Analysis Methods

5.4.1 Study Subjects Disposition

Subject disposition will be summarized by presenting the number of subjects who were enrolled, were included into the ITT and safety populations, received PDT, underwent planned surgery, completed the study and prematurely discontinued with breakdown by the reason for early discontinuation. The analysis will be based on all enrolled subjects.

A listing will be presented to describe whether the subject completed the study, date of completion or early withdrawal, and the reason for early discontinuation, if applicable. A listing will also be provided to describe if the subject meets all inclusion/exclusion criteria. The reason for entry criteria violation, if any, will be presented.

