5.4.6 Photofrin® Injection

All details of Photofrin® injections collected on CRF will be listed.

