5.4.7 Photodynamic therapy

All details of light application collected on CRF will be listed.

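### Does tying treatment-related to the study drug leave out adverse events caused only by the device or the laser light?

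*SAP*

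**What the plan says.** SAP 5.4.11.1 gives the definition: "An AE will be defined as treatment-related if its relationship to the study drug is recorded as" Reasonable Possibility on the CRF. The same section breaks events down by "relationship to study drug (related or not related") and lists each event with its "CTCAE grade, outcome, action taken and drug relatedness". It equates study drug with PHO, the abbreviation for Photofrin, in the treatment-emergent rule ("on or after the date of the study drug (PHO) administration"). SAP 5.1 does the same in the baseline rule ("taken prior to the administration of the study drug (PHO").

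Elsewhere the SAP keeps drug and light apart. The disposition table in 5.4.1 counts subjects who "received PDT, underwent planned surgery" separately from the Safety Population, which the injection alone defines. Section 5.4.6 says that details of the Photofrin "injections collected on CRF will be listed", and 5.4.7 adds: "All details of light application collected on CRF will be listed".

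Protocol 8.4.2 asks the investigator to consider Photofrin, the devices and the laser light. It then gives criteria for a two-level rating of PDT-Photofrin. Protocol 10.5.3 tabulates adverse events by relationship to treatment on the same two levels. The 20% suspension rule, in Protocol 10.1 and SAP 3.1, refers to serious events related to PDT. SAP section 6 declares no departure from the protocol's analyses.

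**The concern.** Safety is the primary objective, and the intervention is a drug activated by light through a fiber placed at bronchoscopy. Some harms could be put down to the light or the fiber placement rather than to the injection. The SAP's own vocabulary separates study drug (PHO) from PDT, so a programmer working to the letter could count only events rated as related to the drug. The related and serious related rows would then describe one part of the treatment while carrying the label treatment-related. Because SAP section 6 declares no change, a reader of the report would have no warning. With about 10 subjects, one omission is visible in a percentage.

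**Working it through.** **The plan's own figures.** The only computed figures nearby are the one-sided 95% upper limits for 0 to 5 events in 10 subjects (Protocol 10.1, SAP 3.1). The exact limit for x events is the 0.95 quantile of a beta distribution with parameters x+1 and 10−x. This gives 0.2589, 0.3942, 0.5069, 0.6066, 0.6965 and 0.7776, which round to the printed 0.26, 0.39, 0.51, 0.61, 0.70 and 0.78. SAP 5.4.11.1 attaches such limits to the table by system organ class and preferred term, which counts treatment-emergent events whatever their rated cause. The relationship flag does not enter them.

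**What is rated.** The opening of Protocol 8.4.2 names three things, but the criteria under both levels have one object, PDT-Photofrin. There is no separate scale for drug, device or light. Protocol 10.5.3 tabulates one relationship with those two levels.

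**What the SAP reads.** Its definition speaks of one relationship per event, takes the protocol's level Reasonable Possibility as the trigger, and says that this is recorded on the CRF. Its listing names one relatedness item. It also excludes the NCS events from the relationship analysis because that item is not collected for them. All this matches one CRF item that carries the protocol's scale.

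**How the SAP uses study drug.** The same section plans a listing of events leading to discontinuation of study drug, although Photofrin is given once (Protocol synopsis). That looks like standard template wording. The opening of Protocol section 8 also speaks loosely of drug-related assessment when it means causality in general. The SAP names the category treatment-related, and SAP 2.2 describes the treatment as one PDT-Photofrin course.

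**A test of the literal reading.** Both documents also use PDT for the light session alone, as when Study Day 3 is called the day of PDT. Read equally literally, the suspension rule would leave out serious events due to the drug only. The terms are loose throughout, so one phrase is weak evidence of a deliberate narrowing.

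**Size under each possible CRF layout.**

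| CRF item | Effect on the related rows |
|---|---|
| One combined PDT-Photofrin rating | 0 subjects change |
| Separate ratings, only the drug rating used | each subject whose only related events are due to device or light drops out: 1/10 = 10 percentage points |
| Drug rating only | the protocol's relationship table could not be built from the data |

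For the second layout the documents give no rate. If p is the assumed chance per subject of having only such events, the expected number missing is 10p and the chance of at least one is 1 − (1 − p)^10. For p = 0, 1, 5, 10 and 20% the expected numbers are 0, 0.1, 0.5, 1 and 2, and the chances are 0, 10, 40, 65 and 89%. These figures rest wholly on the assumed p and the assumed layout, so they are not evidence that either occurs.

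**The case for a change.** The strongest case for a change is that the SAP is meant to hold all specifications, glosses study drug as PHO twice, and treats relationship to study drug as a CRF data point. A combined field is therefore an inference. Attribution to one component is also realistic. The protocol's background links pneumothorax in a pig study to the puncture for fiber placement, and links mucositis to excess light on normal tissue. The SAP's rule of keeping the highest relationship does not say how several component ratings would be combined.

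Much of this is right. The mismatch is real, the CRF cannot be seen, and component attribution can happen. But the pig example involved a chest wall puncture, not the bronchoscopic route used here, so it gives no rate for this trial. The disposition and exposure sections that separate drug from light say nothing about how causality was recorded. A rule for combining ratings is needed only if there are several, and Protocol 8.4.2 provides one scale. A drug-only item would mean that the CRF departed from Protocol 8.4.2, and neither document suggests that it did.

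**Conclusion.** This is an inconsistency of terms that analysts can resolve from the protocol: the relationship item is the rating that investigators were told to make, for PDT-Photofrin. On that reading the number of subjects affected is 0, the SAP's statement of no changes is accurate in substance, and rewording would alter no result.

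The conclusion assumes that the CRF carries one rating on the scale of Protocol 8.4.2. If it does not, the effect is confined to the descriptive related and serious related rows and the breakdown by relationship, at 10 percentage points per affected subject. The primary endpoint is the incidence of adverse events, not of related ones. The all-cause tables, their exact limits and the listing of serious events do not depend on the flag. Neither document runs the suspension rule from this SAP definition: it has its own wording, serious events are monitored in real time (Protocol 8.4.3.1), and a safety board reviews the data (Protocol 8.6). With about 10 subjects and every event listed with its verbatim term, a mislabelled row could be checked by eye. No change to the plan is called for.
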